#### **2.3.1 Tear film stability and volume**

Tear film stability was evaluated automatically by the AI identification system via detection of the first (F-NIBUT) and average noninvasive tear film break-up time (A-NIBUT) using a Placido disc. To assess the lipid layer grade (LLG), the lipid layer interferometric pattern was compared with the lipid layer thickness (LLT) grading scale template provided by the device, which has the following values: 1; LLT < 30 nm; 2, LLT of 30-60 nm; 3, LLT of 60-80 nm and 4, LLT >80 nm. Regarding tear volume, tear meniscus height (TMH) and tear meniscus area (TMA) were also automatically assessed by the AI identification system through focused image of the lower eyelids.

#### **2.3.3 Ocular Hyperemia**

Ocular hyperemia was assessed through complete picture of the ocular surface focused on the bulbar conjunctiva. Nasal ciliary hyperemia (NCIH), temporal ciliary hyperemia (TCIH), nasal conjunctival hyperemia (NCOH) and temporal conjunctival hyperemia (TCOH) were analyzed automatically the AI identification system with a value between 0% (no hyperemia) and 100% (the highest level of hyperemia).

### **2.3.4 Ocular surface staining**

OSS was subjectively and invasively evaluated with the oxford grading schema reported by Bron et al. [27]. Prior to assess OSS, a single drop of unit dose saline was instilled onto a fluorescein-impregnated strip. The right lower lid was then pulled down and the strip was tapped onto the lower tarsal conjunctiva. The same procedure was carried out on the left. A cobalt-blue filter with yellow Kodak Wratten 12 barrier filter was used for a better detection of fluorescein staining.

### **2.3.5 Meibomian gland analysis**

Meibomian gland analysis was performed on the upper and lower eyelid using infrared light after everting the eyelids with a cotton swab. the AI identification system automatically analyzed the meibomian glands, obtaining the upper loss area Meibomian gland (U-LAMG) and lower loss area Meibomian gland (L-LAMG) with a value between 0% (no glandular dropout) and 100% (the highest level of glandular dropout), and upper meibomian gland dysfunction grade (U-MGD grade) and lower meibomian gland dysfunction grade (L-MGD grade), which have the following values: 0, no MGD; 1, mild MGD; 2, moderate MGD and 3, severe MGD.

Meibomian gland secretion was assessed by MGX. Fifteen glands on the lower eyelids were evaluated. For each gland, the secretion had the following scores: 0, no secretion; 1, inspissated/toothpaste consistency; 2, cloudy liquid secretion; and 3, clear liquid secretion. Then, three meibomian gland parameters were assessed: meibomian gland yielding secretion score (MGYSS) (range: 0-45), which was defined as the sum of the grades for all 15 glands, meibomian gland yielding clear secretion (MGYCS) (range: 0-15) and meibomian gland yielding liquid secretion (MGYLS) (range: 0-15).

## **2.4 Combined treatment with MBE, IPL and MGX**

MBE was performed using the yokefellow instrument (Yoke Electronic Corporation, Guangzhou, China), which contains a handpiece with a 1.80 mm diameter medical-grade diamond bur. To ensure a well-tolerated procedure, topical application of 0.1% tetracaine hydrochloride and 0.4% oxybuprocaine hydrochloride was applied. After placing topical anesthetic, a corneal shield was used to protect the ocular surface and a jojoba anesthetic ointment (JAO) (O'Brien Pharmacy, Kansas City, USA) containing 8% lidocaine and 25% jojoba wax were place on the lid margin. Patients underwent MBE on the upper and lower lid margin of both eyes at 500 rpm until complete removal of accumulated biofilm debris, epithelial keratinization or

capped meibomian glands. MBE was carried out only in the first combined treatment session. Immediately after MBE, JAO was cleaned with a cotton swab and IPL was performed.

IPL treatment was carried out with Theraeye Plus (MDS Medical Technologies SL, Barcelona, Spain). The procedure began by applying an ultrasound gel (Carmado SL, Alicante, Spain) to the patient's periocular areas and upper eyelids. In the periocular areas, 6 light pulses were applied; 4 light pulses on the skin below the lower eyelid (with handpiece placed horizontally in the first pass and vertically in the second pass) and 2 light pulses on the canthal area (with handpiece placed vertically in first and second pass). The parameters were as follows: (1) Filter: 650 nm; (2) fluence: 9 j/cm^2; (3) pulses: 2; (4) duration: 3 ms; (5) Delay: 20 ms; and (6) Cooling: 70%. In the upper eyelids, 4 light pulses were applied; 2 light pulses in the first and second pass, respectively. The parameters were as follows: (1) Filter: 650 nm; (2) Fluence: 5 j/cm^2; (3) pulses: 1; (4) duration: 3 ms and (5) Cooling: 70%. Fitzpatrick skin typing [28] was assessed prior to IPL treatment.

Finally, the MGX was realized on both upper and lower eyelids of each eye with a Collins forceps (Medi Instrument Inc, New York, USA). After first combined treatment session, patients were instructed to apply 0.5% dexamethasone sodium phosphate and 1% chloramphenicol topically twice a day during the first week and once a day during the second week. White Sun protection cream was recommended for the first 48 hours in the IPL treatment area.

## **2.6 Statistical analysis**

Statistical analyses were performed with SPSS statistics software, version 26.0 (IBM Corporation, Armonk, NY, USA). The sample size was estimated using the GRANMO calculator, version 7.12 (Municipal Institute of Medical Research, Barcelona, Spain). It was calculated on the basis of assumed mean differences in F-NIBUT and MGYSS between the treatment and control groups at 2 months after the treatment onset, with values of  $3.04 \pm 3.86$  and  $19.75 \pm 5.45$ , respectively. These assumed differences were based on the findings of a pilot study with 16 eyes of 8 patients in each group. With these assumptions, a sample size of 26 eyes per group would yield a power > 80% and a statistically significant paired difference of 95% confidence. Continuous variables were displayed as the mean  $\pm$  standard deviation (SD) with interquartile ranges [IQRs], while ordinal categorical variables were expressed as frequencies (n) and percentages (%). After testing for normality and homogeneity of variance, the paired Student's *t*-test (parametric) or Wilcoxon's signed-rank test (nonparametric) was performed to compare intra-group clinical

outcomes. Within each group, the increment ( $\Delta$ ) was calculated. It was defined as the change from the last visit (LV) to baseline (B) " $\Delta = LV - B$ ". Inter-group clinical outcomes, were analyzed with the unpaired Student's *t*-test (parametric) or Mann-Whitney's U test (nonparametric). Between each group, the differences were calculated as " $\Delta_{Treatment\ group} - \Delta_{Control\ group}$ ". The Pearson's (parametric) or Spearman's Rho correlation coefficient (nonparametric) was used to analyze the correlations between the variables. Stepwise multiple linear regression analysis was performed to detect the influential factors in dry eye symptoms ( $\Delta$ OSDI and  $\Delta$ SANDE). In addition, One-Way ANOVA (parametric) was performed to determine if there were statistically significant differences in  $\Delta$ MGYSS according to baseline L-MGD-grade. A post hoc analysis by Bonferroni's test was carried out to determine statistically significant differences between baseline L-MGD grade. The level of significance was  $P < 0.05$  for all of the comparisons.

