### **2.2 Experimental design**

A flowchart showing the experimental design of the study is presented in Fig.1. Patients with MGD were classified into the treatment and control groups. All patients received a home-based therapy based on Therapearl eye mask warming compress (Bausch & Lomb, Madrid, Spain) twice a day and Eystil synfo

eyedrops (Sifi Iberica SL, Madrid, Spain) 4 times a day during the study including the follow-up period. Treatment group patients also underwent a series of three combined treatment sessions of MBE, IPL and MGX at 2-week intervals. All patients underwent a 2-months follow-up from baseline.

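### The sample-size sentence calls an unpaired between-group comparison 'paired', and its power above 80% holds only if all 26 eyes per group are independent

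*Combined protocol and SAP*

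**What the plan says.** All the sizing text is in section 2.6 of the combined protocol and SAP. The calculation rests on "assumed mean differences in F-NIBUT and MGYSS between the treatment and control groups at 2 months after the treatment onset", given as 3.04 ± 3.86 for F-NIBUT and 19.75 ± 5.45 for MGYSS, and taken from "a pilot study with 16 eyes of 8 patients in each group". The conclusion is that "a sample size of 26 eyes per group would yield a power > 80% and a statistically significant paired difference of 95% confidence".

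The same section assigns the tests. Between groups, outcomes are "analyzed with the unpaired Student's *t*-test (parametric) or Mann-Whitney's U test (nonparametric"). Paired tests appear only within a group: "the paired Student's *t*-test (parametric) or Wilcoxon's signed-rank test (nonparametric) was performed to compare intra-group clinical" outcomes.

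Section 2.2 describes two separate sets of people: "Patients with MGD were classified into the treatment and control groups". Section 2.3 says that every outcome except the two questionnaires is recorded per eye. Section 2.4 describes treatment of the lids of both eyes. Nowhere do the documents give the number of patients behind the 26 eyes, an inter-eye correlation or a design effect.

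**The concern.** Two things in the power sentence do not fit the rest of the plan.

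First, a paired difference needs each treated unit to be matched with a control unit. Here the groups are different patients, and the between-group test is unpaired. A reader cannot tell from the sentence which comparison was powered.

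Second, the sentence counts eyes. Two eyes of one patient share the same tear-film disease, the same home therapy and, in the treatment group, the same sessions. If they are positively correlated, 26 eyes carry less information than 26 independent observations. The power claim is then too high, and a null F-NIBUT result could reflect low power where a reader would take it as evidence of no effect.

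**Working it through.** **Inputs.** From section 2.6: F-NIBUT difference 3.04, SD 3.86; MGYSS difference 19.75, SD 5.45; 26 eyes per group; significance level 0.05. The text does not say what the SDs describe, so I take them as common per-group SDs. It does not state sidedness, so I take two-sided. Eyes per patient is two in the pilot and is not stated for the main study. The inter-eye correlation ρ is not given, so I use 0.3 to 0.9 as an assumed range.

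**Step 1: reproduce the 26.** For F-NIBUT, d = 3.04 / 3.86 = 0.788. The unpaired normal-approximation formula is n per group = 2(z₀.₉₇₅ + z₀.₈₀)² / d² = 2 × (1.960 + 0.842)² / 0.620 = 25.3, rounded up to 26. This matches the plan. For MGYSS, d = 19.75 / 5.45 = 3.62, and the same formula gives 2 × 7.85 / 13.1 = 1.2, or 2 per group. F-NIBUT therefore sets the size.

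**Step 2: power at 26 independent eyes per group.** Noncentrality = d × √(26/2) = 0.788 × 3.606 = 2.84.
- Normal approximation: Φ(2.84 − 1.96) = Φ(0.88) = 81.0%.
- Exact unpaired t-test (noncentral t, 50 df): 79.5%. With 27 per group it is 81.1%.

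**Step 3: was a paired formula used?** With 3.86 as the SD of a paired difference, n = (1.960 + 0.842)² / 0.620 = 12.7, or 13 pairs. That is not 26 per group. The stated size agrees with the unpaired calculation, although a match does not prove which calculator setting was used.

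**Step 4: how much margin is there?** If the 26 eyes are both eyes of 13 patients, the variance of a group mean is multiplied by (1 + ρ), so they are worth 26 / (1 + ρ) independent eyes. Step 1 needs 25.31. Power by the normal approximation stays at 80% only while ρ ≤ 26 / 25.31 − 1 = 0.027.

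**Step 5: patient-level power with 13 patients per group.** The mean of a patient's two eyes has variance SD² × (1 + ρ) / 2. The noncentrality becomes 2.84 / √(1 + ρ), with 24 df for the t-test.

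| Assumed ρ | Noncentrality | Power, t-test on patient means | Power, normal approximation |
|---|---|---|---|
| 0.3 | 2.49 | 67% | 70% |
| 0.5 | 2.32 | 60% | 64% |
| 0.7 | 2.18 | 55% | 59% |
| 0.9 | 2.06 | 51% | 54% |

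The result is below 80% in every row, by either method.

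**The case against.** The strongest reply has four parts.

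- **The arithmetic is sound.** The standard unpaired formula returns 26 with 81.0% power, so the claim is true under the formula that fits it. This stands. The half-point shortfall by the exact t-test is a choice of approximation. The inputs could not support that precision anyway: treating the pilot's 16 eyes per group as independent (30 df), the 95% interval for the SD is 3.86 × √(30/46.98) = 3.08 to 3.86 × √(30/16.79) = 5.16. Over that interval, power at 26 per group runs from about 94% to 55%.
- **'Paired' is a slip of wording.** This is probably right, since the paired formula does not return 26 per group. The slip is still worth correcting, because the sentence is the plan's only statement of which comparison was powered.
- **The 51% to 67% figures belong to a patient-mean test that the plan does not name, and rest on assumed correlations and an assumed two eyes per patient.** The assumptions are real and are labelled as such. The plan's own bilateral treatment, per-eye outcomes and two-eye pilot make them the natural reading. The eye-level test does not rescue the claim. With correlated eyes its standard error is too small and its false-positive rate exceeds 5%. At ρ = 0.5, for example, the nominal cut-off 1.96 acts as 1.96 / √1.5 = 1.60, a two-sided error of about 11%. Power quoted for that test is not comparable with power at a true 5%.
- **The study is reported as complete** (section 2: April 2022 to January 2023). This limits the consequence to how the design and any null result are described. It does not remove the point.

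**Conclusion.** The concern holds in two parts. The label 'paired' contradicts both the contrast that was sized and the planned unpaired test; this needs no assumption. The unqualified power above 80% holds only if all 26 eyes per group are independent. If the main study used both eyes of 13 patients per group, patient-level power is about 67% to 51% for inter-eye correlations of 0.3 to 0.9. That range rests on 3.86 being the per-group SD, a two-sided 5% test, two eyes per patient and the assumed correlations.

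A reader might infer three stronger things that the documents do not support:
- **That 26 is miscalculated, because the exact t-test gives 79.5%.** The figure is reproduced at 81.0% by a standard formula, and the gap is immaterial.
- **That the Mann-Whitney alternative falls clearly short, at about 77.6%.** That figure uses the test's efficiency under normal data (0.955), whereas section 2.6 reserves it for data that fail the parametric assumptions. There its power can be higher than the t-test's.
- **That the plan in effect claims about 97% power, the result for 26 true pairs.** The plan claims only more than 80%, and its separate patient groups rule out that calculation.

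**What to change.** Rewrite the power sentence in section 2.6 along these lines: *For a two-sided unpaired t-test at alpha 0.05, an F-NIBUT difference of 3.04 and a per-group SD of 3.86, 26 eyes per group give 81.0% power by the normal approximation (79.5% by the t-test) if all eyes are independent. The 26 eyes come from [number] patients per group. Allowing for correlation between eyes, power for a comparison of patient means is [values] at inter-eye correlations of [stated range].* If there are 13 patients per group, the values are those in the table above. Confirm that 3.86 is the per-group SD; if it is not, recompute.

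The cost is one rewritten sentence and a patient count that the investigators should already hold. No extra enrolment and no change to data or procedures is asked for. The downside is that the stated power becomes less favourable.

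### The four graded outcomes (LLG, OSS, U-MGD and L-MGD grade) have no inferential method of their own, and the general change-score rule would subtract them without using the baseline grade

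*Combined protocol and SAP*

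**What the plan says.** Three parts of section 2.3 define graded outcomes:

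- LLG (2.3.1): "1; LLT < 30 nm; 2, LLT of 30-60 nm; 3, LLT of 60-80 nm and 4, LLT >80 nm".
- OSS (2.3.4): "OSS was subjectively and invasively evaluated with the oxford grading schema". The grade range is not given.
- U-MGD and L-MGD grade (2.3.5): "0, no MGD; 1, mild MGD; 2, moderate MGD and 3, severe MGD".

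Section 2.6 mentions ordinal variables once, for presentation: "ordinal categorical variables were expressed as frequencies (n) and percentages". For inference it gives one scheme for clinical outcomes:

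- Within groups: "the paired Student's *t*-test (parametric) or Wilcoxon's signed-rank test (nonparametric").
- Increment, Δ = LV − B: "It was defined as the change from the last visit (LV) to baseline (B").
- Between groups: "unpaired Student's *t*-test (parametric) or Mann-Whitney's U test (nonparametric"), with the difference formed as Δ in the treatment group minus Δ in the control group.

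Grades are not exempted. No ordinal model is named, and no between-group comparison is adjusted for baseline. Section 2 states that the study is non-randomized, and section 2.3 states that everything except the two questionnaires is collected per eye.

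**The concern.** A grade label is not an amount, and subtracting two labels causes three difficulties.

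- **Unequal steps.** On the plan's own cut points of 30, 60 and 80 nm, the LLG bands are 30, 30 and 20 nm wide, and the top band is open. A move from 1 to 2 and a move from 3 to 4 both become +1.
- **Bounded scale.** An eye already at the best grade can only score 0 or worse. If it stays there it gets 0, the same as an eye at the worst grade that does not respond.
- **Mismatch of summary and effect.** The table would show n (%) by grade, while the effect would be a difference in grade change that cannot be read from that table.

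The nonparametric route does not repair this, because the subtraction comes before the ranking.

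The rule also leaves the baseline grade unused as a covariate. That costs precision. In a non-randomized comparison it also leaves the result open to baseline differences between the groups. At stake are 4 of the 19 outcomes listed in section 2.3.

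**Working it through.** **1. The plan's own figure.** The sample size uses "assumed mean differences in F-NIBUT and MGYSS between the treatment and control groups". For F-NIBUT (difference 3.04, SD 3.86, two-sided 5%, power 80%):

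n per group = 2 × (1.960 + 0.842)² × (3.86 / 3.04)² = 2 × 7.85 × 1.612 = 25.3, rounded up to 26.

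The stated 26 eyes per group is reproduced (power 81.0% by the normal approximation). MGYSS alone would need 2 per group. No graded outcome enters the calculation, so nothing below changes it.

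**2. Assumed inputs.** The documents give no grade distribution, no baseline to last-visit correlation and no effect for any of the four grades. The following are therefore assumptions:

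- a 4-level grade cut from a bivariate normal latent variable;
- a treatment shift of 0.8 latent SD at the last visit;
- correlation ρ of 0.3, 0.5 or 0.7;
- independent units;
- baseline grade distribution A = 30/35/25/10%, or B = 10/25/30/35% (more eyes at the best grade).

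**3. Tests compared.**

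- Planned: Mann-Whitney on Δ = LV − B.
- Stratified: van Elteren test of last-visit grade within baseline grade, Z = Σ wₖ(Rₖ − E[Rₖ]) / √(Σ wₖ² Var[Rₖ]), with wₖ = 1/(nₖ + 1).
- Linear ANCOVA: last-visit grade, taken as a number, on group and baseline grade.

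**4. Power at 26 units per group** (ρ = 0.3 / 0.5 / 0.7):

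| Distribution | Mann-Whitney on Δ | van Elteren | Gain (points) | Linear ANCOVA |
|---|---|---|---|---|
| A | 58 / 70 / 85% | 74 / 80 / 89% | 16 / 10 / 4 | 78 / 83 / 91% |
| B | 45 / 55 / 71% | 69 / 74 / 85% | 24 / 19 / 14 | 73 / 77 / 87% |

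The first two tests come from 4000 datasets per cell. ANCOVA comes from 2000 datasets per cell on the same model, where the first two tests agreed with the table to within about 3 points. Under the null, Mann-Whitney and van Elteren rejected 4.3 to 5.7% of the time, and ANCOVA 3.9 to 5.8%.

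With 13 units per group (26 eyes reduced to one value per patient, if every patient contributes two), van Elteren gains 3 to 11 points under A and 11 to 14 under B.

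**5. Where the gain comes from.**

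- ANCOVA treats the grades as equally spaced numbers, yet it recovers the whole loss and slightly more.
- An ordinal test without baseline does not keep the power. At ρ = 0.7 under A with 26 per group, Mann-Whitney on last-visit grade had 74%, against 83% for Mann-Whitney on Δ in the same run.
- At ρ = 0.9 under A, power was about 99% for both Mann-Whitney on Δ and van Elteren with 26 per group, and about 81% for both with 13.

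The gain therefore belongs to conditioning on baseline.

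**6. A different model and set of cut points.** Here the shift was 0.8 conditional SD, with three sets of cut points, ρ from 0.3 to 0.9, 26 per group and 600 runs per cell. Proportional-odds regression of last-visit grade on group and baseline grade had 47 to 74% power. Mann-Whitney on Δ had 41 to 56%. The regression was ahead in all 12 scenarios, by 6 to 23 points. The unadjusted last-visit rank test fell from 66–70% at ρ = 0.3 to 18–21% at ρ = 0.9.

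**7. Baseline imbalance.** Assume a 0.5 SD latent baseline difference, no treatment effect, 26 per group, ρ of 0.3 to 0.7, and the same baseline to last-visit relation in both groups. Mann-Whitney on Δ rejected 8 to 15% of the time, and the stratified test 4 to 7%.

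**The case against.** **The subtraction is inferred.** Section 2.6 never says in words that the four grades are subtracted. The sentence on ordinal variables is only a display rule, and the sentence on between-group tests does not say whether Δ or the last-visit value is compared. This stands as a limit on wording. It does not remove the point: the general rule is the only inferential method that reaches these outcomes. If grades were meant to be exempt, they have no stated test. If last-visit grades are compared alone, baseline is still ignored.

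**Ordinality is not what costs power.** A reader might infer that treating grades as numbers loses power that any ordinal analysis would keep, or that linear baseline adjustment would not help. The calculations contradict both.

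**Unequal steps are shown for LLG only.** A reader might extend this to all four grades. The documents give no distances between Oxford grades or between MGD grades.

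**The inputs are assumed.** No loss of power has been demonstrated for this trial, and at high correlation there may be none. This stands in full.

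**The grades are not what the trial is sized on.** This is correct, and it limits the weight of the point.

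**Conclusion.** The point holds in a limited form. Section 2.6 leaves four bounded ordinal outcomes to a general change-score rule. That rule yields an effect that is hard to interpret and makes no use of baseline grade as a covariate.

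With 26 independent units per group, a latent shift of 0.8 SD and correlation 0.3 to 0.7, conditioning on baseline grade gains about 4 to 24 points of power. The gain is illustrative: it depends on assumed distributions and correlations and can vanish at 0.9. The protection against false positives from baseline imbalance rests on a common baseline to last-visit relation in the two groups, which a non-randomized design does not guarantee.

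The case for an ordinal model is interpretability: its effect measure matches graded data and the n (%) display. The case for adjustment is power and baseline imbalance. The documents do not support a claim that the sample size is wrong or that the F-NIBUT and MGYSS analyses are affected by this point.

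**What to change.** For LLG, OSS, U-MGD grade and L-MGD grade, amend section 2.6 as follows:

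- Replace the Δ contrast with a between-group comparison of last-visit grade conditional on baseline grade.
- Use proportional-odds regression on group and baseline grade, and report the common odds ratio with its 95% CI.
- Account for two eyes per patient, for example by ordinal GEE, patient-clustered standard errors, or one value per patient.
- If a rank P-value is wanted, use the van Elteren test stratified by baseline grade, on one unit per patient only, pooling sparse strata.
- Show the baseline by last-visit grade table as n (%) in each group.

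The cost is a few lines of plan text and a little more analysis work; no new data are needed. There are two drawbacks. The odds ratio relies on proportional odds. Its likelihood-ratio test is also slightly liberal at this size: 6 to 7% in one simulation, and in a 600-run null check 5.3% with a linear baseline term and 7.5% with a categorical one. The sample size does not change.

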### **2.1 Subjects**

Patients with DED due to MGD attending Novovision Ophthalmology Clinic were enrolled. The inclusion criteria were as follows: (1) age  $\geq$  18 years old; (2) DED diagnosis according to DEWS II [25] meeting one of the following conditions: (2.1) ocular surface disease index (OSDI) score  $\geq$  13; (2.2) NIBUT  $<$  10 seconds; and (2.3) ocular surface staining with  $>$  5 or 9 corneal or conjunctival stains, respectively, and (3) MGD diagnosis according to the international workshop on MGD [26] meeting two of the following conditions: (3.1) irregularity of the eyelid margin or mucocutaneous junction; (3.2) vascularity of the eyelid margin; (3.3) plugged or capped Meibomian gland orifices; (3.4) Meibomian gland atrophy; or (3.5) decreased meibum quality and quantity. The exclusion criteria included: (1) skin pathologies that prevent IPL treatment; (2) all corneal disorders that affect diagnostic tests, such as: (2.1) active corneal infections; and (2.2) corneal dystrophies; (3) active ocular allergy; (4) pregnant or lactating women; and (5) patients who did not understand or comprehend the informed consent. Systemic or ocular diseases, previous systemic or ocular treatments and ocular surgeries with more than 6 months of postoperative evolution were not considered exclusion criteria to better reflect the patient population. Contact lens users were instructed not to wear their contact lenses one week before baseline and follow-up examinations.

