### **2.3 Clinical assessment**

Parameters were assessed with the S390L Firefly WDR slit lamp (Shangai Mediworks Precision Instruments Co. Shangai, China) that includes a dry eye module designed to perform objective and non-invasive measures, which are analyzed by an artificial intelligence (AI) identification system (Mediview R3.0 software). To assess treatment efficacy, parameters were measured at baseline and the last visit. DED symptoms were assessed with the ocular surface disease index (OSDI) and symptom assessment in dry eye (SANDE) questionnaires. Ocular surface measurement was carried out by one examiner ([name]) in the following sequence to best preserve the integrity of the tear film to avoid affecting the test results: (1) tear film stability and volume; (2) ocular hyperemia; (3) ocular surface staining (OSS) and (4) meibomian gland analysis. Except for OSDI and SANDE questionnaires, which were collected per subject, all other clinical outcomes were collected per eye. To evaluate treatment safety, post-treatment adverse events were reported.

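### Section 2.6 tests the before-after change within each group alongside the between-group comparison without saying which decides efficacy; a within-group P value cannot show that MBE, IPL and MGX add anything to the shared home therapy.

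*Combined protocol and SAP*

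**What the plan says.** - **Treatment (Section 2.2).** The home therapy is common to both groups: "All patients received a home-based therapy based on Therapearl eye mask warming compress" twice a day, with lubricant drops "4 times a day during the study including the follow-up period". The groups differ by the added sessions: "Treatment group patients also underwent a series of three combined treatment sessions of MBE, IPL and MGX at 2-week intervals". On duration: "All patients underwent a 2-months follow-up from baseline". No run-in or washout is described.
- **Entry (Section 2.1).** Dry eye disease is established by "meeting one of the following conditions: (2.1) ocular surface disease index (OSDI) score" of at least 13, NIBUT below 10 seconds, or staining above a threshold. One of the three is enough. Previous ocular treatment is not an exclusion.
- **Measurement (Section 2.3).** "To assess treatment efficacy, parameters were measured at baseline and the last visit".
- **Analysis (Section 2.6).** A paired t-test or Wilcoxon signed-rank test "was performed to compare intra-group clinical" outcomes. An unpaired t-test or Mann-Whitney test compares the groups, and the between-group difference is calculated as the change in the treatment group minus the change in the control group. One significance level, P < 0.05, covers every comparison. No primary outcome or deciding comparison is named.
- **Objective and design (Sections 1 and 2).** The aim is to learn whether the combination leads to improved symptoms and signs; that sentence names no comparator. The study is unmasked and non-randomized, with a control group.

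**The concern.** The treatment group's change from baseline to last visit has several possible sources besides MBE, IPL and MGX:

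- two months of compresses and drops;
- regression to the mean on whichever measure qualified the patient;
- expectation in an unmasked study, which matters most for OSDI and SANDE.

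A paired test asks whether anything changed over two months and cannot apportion the change among these sources. Nor is a significant result in the treatment group alongside a non-significant one in the control group a test of the difference between them, because two groups with the same true change can easily fall on opposite sides of 0.05.

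Because the objective is worded as improvement and no comparison is given precedence, a significant paired test could be reported as answering it. At stake is a positive efficacy claim when the added treatment does nothing.

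**Working it through.** **1. The plan's own figure.** Inputs from Section 2.6: an F-NIBUT difference between groups of 3.04 with SD 3.86, 26 eyes per group, and power above 80%. Two-sided 5% is assumed, since the section does not state sidedness.

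- Two-sample formula: n = 2 × (1.960 + 0.842)² × 3.86² / 3.04² = 25.3, so 26 per group. Power at 26 is 81.0%.
- One-sample (paired) formula: n = (1.960 + 0.842)² × 3.86² / 3.04² = 12.7, so 13.

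The 26 comes from the two-sample formula. The study was sized for the between-group contrast, although Section 2.6 calls the detectable difference paired.

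**2. How often the paired test is significant with no added effect.** Assumptions: SD of change 3.86 s (the documents give this figure for the between-group comparison, not expressly as an SD of change), and a shared mean rise of 1, 1.5 or 2 s in both groups. The documents give no figure for the shared rise. The test statistic follows a noncentral t with n − 1 degrees of freedom and noncentrality (rise / 3.86) × √n. The critical value is 2.060 for n = 26 and 2.179 for n = 13 (26 eyes as 13 patients). With p the probability of significance in one group, treatment significant and control not has probability p(1 − p).

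| n per group | Shared rise (s) | Noncentrality | p | p(1 − p) |
|---|---|---|---|---|
| 26 | 1.0 | 1.321 | 24.6% | 18.5% |
| 26 | 1.5 | 1.981 | 47.8% | 25.0% |
| 26 | 2.0 | 2.642 | 71.9% | 20.2% |
| 13 | 1.0 | 0.934 | 13.8% | 11.9% |
| 13 | 1.5 | 1.401 | 25.2% | 18.9% |
| 13 | 2.0 | 1.868 | 40.5% | 24.1% |

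**3. The between-group test in the same situation.** The shared rise cancels, so the error rate is about 5% whatever its size, for comparable groups and independent eyes. In a simulation of 13 patients with two eyes each per group, analysed as 26 independent eyes, the rate was 11% at a between-eye correlation of 0.5 and 15% at 0.8.

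**4. Regression to the mean on NIBUT.** Assumptions: single-reading SD 3.86 s, mean 8 or 10 s, reliability r of 0.5 to 0.85, and the qualifying reading is also the analysed baseline. Let z = (10 − mean) / 3.86, let φ and Φ be the normal density and distribution function at z, and let q be the share of patients who would qualify on another criterion, independently of NIBUT.

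Expected rise = (1 − r) × 3.86 × φ × (1 − q) / [Φ + q(1 − Φ)]

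- q = 0 (everyone enters on NIBUT): smallest 0.15 × 3.86 × 0.3488 / 0.6978 = 0.29 s; largest 0.5 × 3.86 × 0.3989 / 0.5 = 1.54 s.
- q = 0.5: 0.12 to 0.51 s.
- q = 0.8: 0.04 to 0.17 s.

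Section 2.1 needs only one criterion, so the range of 0.3 to 1.5 s is an upper case. Steps 2 and 4 use 3.86 s in different roles (SD of change, SD of one reading), which agree before selection only at r = 0.5. They are separate illustrations, not one model.

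**The case against.** The strongest reply is that the plan already contains the remedy. It has a concurrent control group on the same home therapy, it calculates the treatment change minus the control change, and it is sized on a between-group difference. That is correct. A reader might infer that the before-after test is the only efficacy analysis; Section 2.6 does not support that. A reader might also infer that the plan intends to claim efficacy from within-group P values. No sentence says so: Section 2.6 lists the tests without ranking them, and the statement in Section 2.3 that "parameters were measured at baseline and the last visit" fixes visit timing, with those values feeding both kinds of comparison. What stands is that nothing says which comparison decides.

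A second reply is that a start of home therapy at baseline is inferred. It is. Section 2.2 says it is given during the study and counts follow-up from baseline, so this is the natural reading, but no start day is stated and earlier use of similar care is not excluded. If some patients were already using it, the shared change would be smaller. Regression to the mean and expectation would remain, so a run-in alone would not turn the paired test into evidence of an added effect.

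Third, the 1 to 2 s rise is assumed and the percentages follow from it. That is so; they show what can happen and do not forecast this study.

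Finally, dropping within-group P values is partly a reporting preference. Naming the deciding comparison is the essential step, but removing the P values takes away the means of misreading.

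**Conclusion.** The point holds as an unranked pair of analyses, one of which cannot address the added effect of MBE, IPL and MGX. It does not hold as a claim that the study lacks a suitable contrast. Neither a within-group P value nor a contrast of the two groups' within-group P values is evidence of an added effect.

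Under the stated assumptions, with no added effect, the treatment group's paired test is significant in 25% to 72% of studies with 26 independent units and in 14% to 41% with 13. The pattern of treatment significant and control not appears in roughly 12% to 25%. That the shared rise would be as large as 1 to 2 s cannot be established from the documents, and regression to the mean supplies up to about 1.5 s only if every patient qualifies on NIBUT.

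A reader might infer that the between-group test is safe at 5% as planned. The documents do not support that either: allocation is not random, outcomes are collected per eye, and only the treatment group has the topical dexamethasone and chloramphenicol described in Section 2.4. Those are separate issues. They limit the between-group result but do not rescue the paired tests. The change is worth making, and it is a matter of wording rather than design.

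**What to change.** In Section 2.6:

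1. State that efficacy is judged only on the between-group difference in change, which the plan already calculates, reported with its 95% CI.
2. Report within-group changes descriptively, as mean change with CI and no P value.
3. State that no efficacy conclusion will be drawn from significance within one group, or from one group's paired test being significant and the other's not.

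The cost is a few sentences and one set of before-after P values; no further patients, visits or measurements are needed. The downside is that a favourable before-after P value can no longer be quoted as efficacy. The change does not resolve non-random allocation or the use of two eyes per patient, which need their own handling in the between-group analysis.
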